# 10.3. Lost to Follow-Up

A subject will be considered lost to follow-up if he or she repeatedly fails to return for scheduled visits and is unable to be contacted by the study site.

The following actions must be taken if a subject fails to return to the clinic for a required study visit:

- The site must attempt to contact the subject and reschedule the missed visit as soon as possible and counsel the subject on the importance of maintaining the assigned visit schedule and ascertain whether or not the subject wishes to and/or should continue in the study.
- Before a subject is deemed lost to follow up, the investigator or designee must make every effort to regain contact with the subject (where possible, 3 telephone calls and, if necessary, a certified letter to the subject's last known mailing address or local equivalent methods). These contact attempts should be documented in the subject's medical record.
- Should the subject continue to be unreachable, he/she will be considered to have withdrawn from the study with a primary reason of lost to follow-up.

## 11. ADVERSE EVENTS

The definitions of an AE or SAE is provided in Appendix 2.

AEs will be reported by the subject (or, when appropriate, by a caregiver, surrogate, or the subject's legally authorized representative).

The investigator and any designees are responsible for detecting, documenting, and recording events that meet the definition of an AE or SAE and remain responsible for following up AEs that are serious, considered related to the study treatment or study procedures, or that caused the subject to discontinue the study (see Appendix 2).

# 11.1. Time Period and Frequency for Collecting AE and SAE Information

All AEs and SAEs will be collected from the signing of the ICF until the safety follow-up visit at Day 42 at the time points specified in the Schedule of Events.

All SAEs will be recorded and reported to the sponsor or designee within 24 hours, as indicated in Appendix 2. The investigator will submit any updated SAE data to the sponsor within 24 hours of it being available.

Investigators are not obligated to actively seek AE or SAE in former study subjects. However, if the investigator learns of any SAE, including a death, at any time after a subject has been discharged from the study, and he/she considers the event to be reasonably related to the study treatment or study participation, the investigator must promptly notify the sponsor.

The method of recording, evaluating, and assessing causality of AE and SAE and the procedures for completing and transmitting SAE reports are provided in Appendix 2.

# 11.2. Methods of Detecting AEs and SAEs

Care will be taken not to introduce bias when detecting AEs and/or SAEs. Open-ended and non-leading verbal questioning of the subject is the preferred method to inquire about AE occurrences.

# 11.3. Follow-up AEs and SAEs

After the initial AE/SAE report, the investigator is required to proactively follow each subject at subsequent visits/contacts. All SAEs will be followed until resolution, stabilization, the event is otherwise explained, or the subject is lost to follow-up (as defined in Section 10.3), or the subject is withdrawn from the study due to clinical deterioration precluding the subject's safe participation in the study (as defined in Section 10.2). Further information on follow-up procedures is given in Appendix 2.

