- Continue offloading applied in accordance with Appendix 6

If the ulcer remains open at visit 7, subjects will be given a supply of non-abrasive bandages and written instructions on weekly ulcer care until the Day 42 follow up visit (Visit 8). In addition, subjects will be told to call if there is any worsening of the ulcer with regard to pain, signs of infection, or swelling.

Standardized offloading will continue until the final study visit (Day 42±2 days) regardless of wound healing status.

Visit 8 (Day 42±2) End of Study (EOS) Visit: The subject shall attend final end-of-study 42±2 days post

Randomization. At this follow-up visit, the subject will undergo the following procedures and evaluations.

- Vital signs measurements including weight, temperature, resting blood pressure, heart rate, and respiratory rate. Vital signs are to be obtained prior to collecting laboratory samples
- 12 Lead ECG
- Physical examination
- Safety Laboratory Tests
- For females of child-bearing potential: pregnancy test (serum) to be performed
- Ulcer Assessment: Visual examination of chronic ulcer.
- Take digital photos with the digital camera provided by sponsor. Two photos are to be taken from a focal distance of 18 inches, and one photo taken close-up for a total of three digital images
- Employ an advanced digital imaging system to accurately measure the target foot ulcer dimensions
- Record all adverse events (local and systemic), concurrent procedures, and changes in concomitant medications during the study on the source documents and case report forms (eCRFs)
- Physician may perform or not perform debridement according to his practice standards
- Offloading ends

Early Termination Visit: If a subject withdraws prior to completing the study, the reason for withdrawal will be documented. If a subject withdraws early due to a Serious Adverse Event, he/she will be followed until resolution/stabilization of the SAE.

If a subject prematurely withdraws from the study, subject will be asked to complete the study procedures and evaluations performed in the final study visit at the time of withdrawal from the study:

- Vital signs measurements including weight, temperature, resting blood pressure, heart rate, and respiratory rate. Vital signs are to be obtained prior to collecting laboratory samples
- 12 Lead ECG
- Physical examination
- Safety Laboratory Tests
- For females of child-bearing potential: serum pregnancy test to be performed.

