# 10.2. Withdrawal from the Study

A subject may withdraw from the study at any time at his/her own request or may be withdrawn at any time at the discretion of the investigator for safety, behavioral, compliance, or administrative reasons.

If the subject withdraws consent for disclosure of future information, the sponsor may retain and continue to use any data collected before such a withdrawal of consent.

If a subject withdraws from the study, he/she may request destruction of any samples taken and not tested, and the investigator must document this in the site study records.

See Schedule of Events for data to be collected at the time of study discontinuation and follow-up and for any further evaluations that need to be completed

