# **Trial Stopping Rules**

Subjects will be permitted to withdraw at any time and investigators can withdraw a patient based on the occurrence of an AE/SAE interfering with treatment or placing the subject's health in jeopardy, or pause treatment for any one these scenarios: (a) wound gangrene; osteomyelitis; G3-4 AE; SAE related to study drug. Occurrence of ≥3 of the above criteria in any given cohort will also require a pause in treatment for the cohort, with subsequent actions determined based on the DMC charter.

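### Section 11.3 lets SAE follow-up end when a subject is withdrawn for clinical deterioration, which contradicts the Early Termination rule and Section 11, so the final outcome of a severe case may go uncollected

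*Protocol*

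**What the plan says.** Four places in the protocol bear directly on when follow-up of an SAE ends.

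- **Section 11.3 (Follow-up AEs and SAEs)** starts with the usual end points: "All SAEs will be followed until resolution, stabilization, the event is otherwise explained, or the subject is lost to follow-up". The same sentence then adds one more alternative, that "the subject is withdrawn from the study due to clinical deterioration precluding the subject's safe participation in the study (as defined in Section 10.2").
- **Section 8, Early Termination Visit**: "If a subject withdraws early due to a Serious Adverse Event, he/she will be followed until resolution/stabilization of the SAE".
- **Section 11 (Adverse Events)** says that investigators "remain responsible for following up AEs that are serious, considered related to the study treatment or study procedures, or that caused the subject to discontinue".
- **Section 10.2 (Withdrawal from the Study)**, to which Section 11.3 refers, says that a subject "may be withdrawn at any time at the discretion of the investigator for safety, behavioral, compliance, or administrative reasons".

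The SAP uses the information at stake. Its Analysis section asks the report to give, for each SAE, a short description, how it resolved and its effect on the study. Its Trial Stopping Rules also foresee withdrawals driven by adverse events: "investigators can withdraw a patient based on the occurrence of an AE/SAE interfering with treatment or placing the subject's health in jeopardy".

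**The concern.** In Section 11.3 the withdrawal clause is joined to the other end points by an or, so it is sufficient on its own. The SAE need not have resolved or stabilized. The Early Termination text and Section 11 both point the other way for the same kind of subject, and neither makes an exception for deterioration.

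Consider a subject whose foot infection becomes an SAE and worsens, and who is withdrawn during treatment. Under Section 11.3 the site may stop following the event once withdrawal takes effect. Under the Early Termination text it must continue until the event resolves or stabilizes.

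Safety is the primary objective, and the clause applies to the subjects who are doing worst. If it is used, the missing outcomes are those of severe cases, and the SAE narratives that the SAP calls for would have no ending for them. With up to five sites, different sites could also handle the same situation differently.

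**Working it through.** No figure in the plan bears on this point and no formula applies. The check is to set the governing texts side by side for one case: an SAE that is unresolved and not stable, in a subject withdrawn because of it.

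| Protocol text | Does follow-up of that SAE continue after withdrawal? |
|---|---|
| Section 11.3 | It may stop. Withdrawal for deterioration is a listed end point. |
| Section 8, Early Termination Visit | Yes, until resolution or stabilization. |
| Section 11 | Yes. The event is serious and caused discontinuation, and the duty covers both. |
| Section 10.2 | Silent on follow-up of events. |
| Appendix 2, Follow-up of AEs and SAEs | Requires further evaluations as indicated and prompt updates, but gives no end point. |
| Section 11.1 | Investigators need not actively look for events in former subjects. They notify a later SAE if they learn of it and consider it reasonably related. |

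**Step 1: the conflict.** The first three rows give incompatible answers for the same subject. Section 11.3 sends the reader to Appendix 2 for further procedures, but Appendix 2 does not settle which answer applies.

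**Step 2: the cross-reference.** The sentence in Section 11.3 also cites Section 10.3 for loss to follow-up, and Section 10.3 does define that. Section 10.2 has no matching definition of clinical deterioration. It offers safety as one of several discretionary reasons. The trigger for ending follow-up is therefore left to judgment.

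**Step 3: comparison with similar rules.** Section 11.5.4 has clinically significant laboratory abnormalities recorded as adverse events repeated until they return to normal or baseline or cease to matter clinically, with no exception for withdrawal. Appendix 1 withdraws a subject who becomes pregnant but keeps following her after delivery. Read literally, a laboratory adverse event that is not serious could be followed for longer than an SAE in a subject who deteriorated.

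**Step 4: what is lost and what is not.** Section 11.1 requires SAEs to be reported within 24 hours, and the Early Termination visit collects vital signs, ECG, physical examination, laboratory tests and wound assessments. The event is therefore in the database before the clause can operate. The SAP's primary endpoint analysis is a summary of the incidence of treatment-emergent adverse events, and that subject is already counted. What can be missing is how the event ended, which is the item the SAP lists for each SAE.

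**The case against.** The strongest reply is that the protocol already requires continued follow-up in two other places. The Early Termination text is the more specific rule and is what a site would use at withdrawal, so a careful site would lose nothing. It could also be said that Section 8 speaks of a subject who withdraws, whereas Section 11.3 speaks of one who is withdrawn, and that each rule has its own case.

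The first part stands to this extent: Section 11.3 permits the loss and does not make it certain. The second part does not remove the conflict. The duty in Section 11 covers events that caused discontinuation, whoever made the decision, and the Schedule of Events has one Early Termination column for all early leavers. It is also fair to say that the safety reason in Section 10.2 is broad enough to cover deterioration. The reference is loose rather than empty, but it does not supply the definition that it promises.

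A reader might infer more than the documents support:

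- **That event rates by arm would shift.** They would not for the event concerned, because it has been recorded and counted.
- **That planned observation days are lost through this clause.** Those days are lost because the subject left the study. The clause governs only SAEs already reported.
- **That new serious events after the Early Termination visit go uncollected because of it.** Genuinely new events fall under the former-subject rule in Section 11.1, which changing Section 11.3 would leave as it is.
- **That the escalation decision would be distorted.** The dose-limiting toxicity criteria are in a Data Monitoring Committee charter that is not among these documents, and the pause criteria act when an event occurs. Nothing shows that the decision turns on how an SAE finally ends.

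**Conclusion.** The point holds as an internal contradiction of moderate severity. Section 11.3 allows follow-up of an unresolved SAE to end at a withdrawal for clinical deterioration. Section 8 (Early Termination Visit) and Section 11 require it to continue, and the definition cited in Section 10.2 is not there.

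The effect is confined to the final outcome of an SAE in a subject withdrawn for deterioration, and arises only if a site acts on Section 11.3 rather than the other two texts. The incidence count for that event does not change and no planned analysis is altered. The documents give no basis for estimating how many subjects would be affected, so no number is offered. The conclusion assumes that the deterioration is itself an SAE or accompanies an ongoing one; otherwise the texts do not collide.

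It still merits correction, because the plan intends to report SAE resolution and the rule as written lets that information be missing for the sickest subjects.

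**What to change.** Reconcile Protocol Sections 8 (Early Termination Visit), 10.2, 11 and 11.3 so that a single end point for collecting SAE outcomes applies throughout. One way is to remove the deterioration-withdrawal clause from Section 11.3, which would bring it into line with Section 8 and Section 11. That edit would also remove the reference to Section 10.2. If the sponsor keeps the clause, the term needs a definition at the place cited, and Sections 8 and 11 need a matching exception.

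This concerns the collection of outcome data only. It takes no position on when a subject should stop treatment or be withdrawn. No change to the SAP is needed: its Trial Stopping Rules do not address SAE follow-up.

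The cost is one clause in a protocol amendment. If the clause is removed, sites take on no follow-up beyond what Sections 8 and 11 already ask of them.

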## 11.3.1. Regulatory Reporting Requirements for SAEs

- Prompt notification by the investigator to the sponsor of a SAE is essential so that legal obligations and ethical responsibilities towards the safety of subjects and the safety of a study treatment under clinical investigation are met.
- The sponsor has a legal responsibility to notify both the local regulatory authority and other regulatory agencies about the safety of a study treatment under clinical investigation. The sponsor will comply with country-specific regulatory requirements relating to safety reporting to the regulatory authority, Institutional Review Boards (IRB)/Independent Ethics Committees (IEC), and investigators.
- Investigator safety reports must be prepared for suspected unexpected serious adverse reactions (SUSAR) according to local regulatory requirements and sponsor policy and forwarded to investigators as necessary.
- An investigator who receives an investigator safety report describing a SAE or other specific safety information (e.g., summary or listing of SAEs) from the sponsor, will review and then file it along with the Investigator's Brochure and will notify the IRB/IEC, if appropriate according to local requirements.

# 11.4. Pregnancy

Details of all pregnancies in female subjects and female partners of male subjects, will be collected after the start of study treatment and until 14 days (+/- 2 days) after last dose of study drug (during the safety follow up visit).

If a pregnancy is reported, the investigator should inform the sponsor within 24 hours of learning of the pregnancy and should follow the procedures outlined in Appendix 1.

Abnormal pregnancy outcomes (e.g., spontaneous abortion, fetal death, stillbirth, congenital anomalies, ectopic pregnancy) are considered SAEs.

# 11.5. Safety Assessments

Planned time points for all safety assessments are provided in Schedule of Events.

## 11.5.1. Physical Examinations.

Physical exams are conducted per institutional protocol. At minimum, the following system are to be reviewed:

- Ear, nose and throat (EENT)
- Cardiovascular
- Respiratory
- Gastrointestinal (GI)

- Musculoskeletal/Connective Tissue
- Neurological
- Endocrine/Metabolic
- Hematopoietic/Lymphatic

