## 3.2. Benefit/Risk Assessment

More detailed information about the known and expected benefits and risks and reasonably expected adverse events of LA-Bisphosphocin-Nu-3 gel may be found in the Investigator's Brochure.

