- The caregiver will be observed applying the first dose in the clinic to ensure compliance administering Test Product topically to the diabetic foot ulcer and surrounding intact skin. The target ulcer will be dressed with Mepitel, or equivalent, which will be trimmed to cover the entire dimension of the ulcer and overlaid into the ulcer, followed by Tegaderm dressing covering the entire dimension of the ulcer. Padding and Coban Lite 2- layer dressing or equivalent will be placed over the Mepitel, or equivalent, covered with Tegaderm
- The subject will be scheduled for the next study visit, with a reminder to bring the test article kit, including all tubes, whether they are empty, partially empty and/or unused tubes to the visit
- Record all adverse events (local and systemic), concurrent procedures, and changes in concomitant medications during the study on the source documents and case report forms (eCRFs)
- Continue offloading applied in accordance with Appendix 6

Visit 4 (Day 7±2 days.): Subjects will return after applying test product for 7 (+/- 2) days every 12 hours. Subject disease assessments will be performed as specified in the schedule of events table.

- Vital signs measurements: Weight, temperature, resting blood pressure, heart rate, and respiratory
- Ulcer Assessment: Visual examination of chronic ulcer before and after light debridement (if necessary)
- Light debridement, only if required
- Digital images should be taken pre and post debridement with the sponsor provided digital camera, if debridement is required. Two photos are to be taken from a focal distance of 18 inches, and one photo taken close-up for a total of three digital images
- Employ an advanced digital imaging system to accurately measure the target foot ulcer dimensions following debridement (if debridement is required)
- Collect Test Product kit dispensed on Day 0, determine accountability
- Subjects will be provided with his/her second designated test product kit and instructed to apply the product twice daily for 1 week (7±2 days)

- Two wound swabs, one for culture and one for microflora examination are taken BEFORE debridement, if the wound is still open
- The subject will be scheduled for the next study visit, with a reminder to bring the test article kit and tubes, including empty, partially used, and unused tubes to the visit

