# APPENDIX 2: ADVERSE EVENTS DEFINITIONS AND PROCEDURES FOR RECORDING, EVALUATING, FOLLOW-UP, AND REPORTING

#### **Definition of AE**

An AE is any untoward medical occurrence in a subject or clinical study subject, temporally
associated with the use of study treatment, whether or not considered related to the study
treatment.

Note: An AE can therefore be any unfavorable and unintended sign (including an abnormal laboratory finding), symptom, or disease (new or exacerbated) temporally associated with the use of study treatment. Local reactions to test product administration include but are not limited to pain, edema, rash, cellulitis, localized infectious processes, and any systemic reaction including fever, allergic reaction, and anaphylaxis, and would be considered to be AEs.

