  - Laboratory evaluations and vital signs assessments will be summarized by dose group (including placebo group) and time point of collection (i.e., visit number starting with randomization visit) (see shell Table 2).
    - Tables will also be constructed for each subject per timeline (see Shell Table 3)

[figure not shown]
SAP: LLA-Nu3-CLIN002 Page 8 of 21

 Table describing change in value and percentage change from baseline for each visit will be provided for vital signs for each subject (see Shell Table 4)

- Table describing out-of-normal range shifts will be provided for clinical laboratory results for each subject, grouped according to dose group (See Shell Table 5)
- Table describing changes noted in physical examinations (at each visit after randomization) will be constructed for each subject, grouped according to dose group (see Shell Table 6)
- Efficacy date will be analyzed as follows:
  - Summary statistics of DFUs that healed by treatment group by 6 weeks (numbers and percentage healed); graph showing weekly percentage of wounds healed by treatment group
  - PAR weekly plot by treatment group; summary table of PAR values by week and treatment group
  - Time to heal within 6 weeks (summary time to heal statistics by treatment group) using Kaplan-Meier method; probability of wound healing (1-survival ≡ 1-wounds not healed) plot by treatment group. If the percentage healed figures for the 5% and 10% Nu-3 groups at 6 weeks is within 10% and a statistical power calculation shows that the proportions of wounds healed for the combined versus placebo groups is at least 80%, the times to heal will be tested using the logrank test.
  - Bacterial counts (CFU/g) for weeks 0-4 will be analyzed by (a) reporting the means and standard deviations for each group at each time point and (b) using GLMM (general linear modeling with repeated measures [weeks 1-4] and counts at week 0 as a factor)
  - Microbiological data will be summarized for each of the 3 treatment groups for each visit (visits 1, 3, 4, 5, 6, 7; unscheduled visit; early termination) as follows (a) list of species detected in each microbiological sample (Shell Table 11); and (b) susceptibility testing to the following drugs for each microbiological sample: penicillin, vancomycin, and linezolid (Shell Table 12)
    - \*A reason will be given in each instance in which susceptibility testing was *not* done (e.g., no growth).

SAP: LLA-Nu3-CLIN002 Page 9 of 21

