{Continue for all scheduled			
post-baseline visits and all			
analytes. Start a new page for			
every additional analyte}			
Subject ID	XX-XXX	XX-XXX	XX-XXX
<vital (unit)="" sign*=""></vital>			
Visit 1			
Value	XX.X	XX.X	xx.x
Subject ID	XX-XXX	XX-XXX	XX-XXX
<vital (unit)="" sign=""></vital>			
Visit 2			
Value	XX.X	xx.x	XX.X
{Continue for all scheduled			
post-baseline visits and all			
vital signs. Start a new page			
for every additional vital sign}			

Nu-3: bisphosphocin Nu-3 gel; \*some vital signs will be paired—for example, blood pressure

SAP: LLA-Nu3-CLIN002 Page 13 of 21

Shell Table 4. Changes in vital signs assessments for each subject by treatment group and visit number compared to randomization visit [1].

Vital Signs Visit	Nu-3 (5%)	Nu-3 (10%)	Placebo
Statistic			
Subject ID	XX-XXX	XX-XXX	XX-XXX
<vital (unit)="" sign*=""></vital>			
<visit 1,="" value=""></visit>	XX.X	xx.x	XX.X
<visit 2,="" change="" in="" sign="" vital=""></visit>	(-) xx.x	(-) xx.x	(-) xx.x
<visit 2,="" change="" in<="" percentage="" td="">(-) xx.x%	(-) xx.x%	(-) xx.x%	</visit>	(-) xx.x%	(-) xx.x%	(-) xx.x%
vital sign>			
{Continue for all scheduled			
post-baseline visits and all			
vital sign changes.}			
{Continue for all scheduled			
post-baseline visits and all			
vital signs. Start a new page			
for every additional vital sign}			

Nu-3: bisphosphocin Nu-3 gel; \*some vital signs will be paired—for example, blood pressure

SAP: LLA-Nu3-CLIN002 Page 14 of 21

Shell Table 5. Out of normal range shifts for laboratory evaluations for each subject by treatment group and visit number; randomization visit=1.

Analyte Visit	Nu-3 (5%)	Nu-3 (10%)	Placebo
Statistic			
Subject ID	XX-XXX	XX-XXX	XX-XXX
<analyte (unit=""></analyte>	70.700		7017001
Visit 1			
Missing	Y/N	Y/N	Y/N
Low	y/N	Y/N	, Y/N
Normal	y/N	Y/N	y/N
High	Y/N	Y/N	Y/N
Subject ID	XX-XXX	XX-XXX	XX-XXX
<analyte (unit=""></analyte>			
Visit 2			
Missing	Y/N	Y/N	Y/N
Low	Y/N	Y/N	Y/N
Normal	Y/N	Y/N	Y/N
High	Y/N	Y/N	Y/N
{Continue for all scheduled			
post-baseline visits and all			
analytes. Start a new page for			
every additional analyte}			

Nu-3: bisphosphocin Nu-3 gel

SAP: LLA-Nu3-CLIN002 Page 15 of 21

Shell Table 6. Changes noted in physical examinations for each subject by treatment group and visit number; randomization visit=1. If there is no change, entry will be blank.

Physical Exam Change Visit	Nu-3 (5%)	Nu-3 (10%)	Placebo
Description			
Subject ID	XX-XXX	XX-XXX	XX-XXX
Visit 1*			

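### No systematic skin examination is required in this topical-gel safety trial, and the SAP's physical-examination table would show unexamined visits as unchanged

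*Protocol*

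**What the plan says.** **Physical examination.** Protocol Section 11.5.1 states: "Physical exams are conducted per institutional protocol". It then sets a floor, "At minimum, the following system are to be reviewed", and lists eight systems: ear, nose and throat; cardiovascular; respiratory; gastrointestinal; musculoskeletal and connective tissue; neurological; endocrine and metabolic; hematopoietic and lymphatic. The Schedule of Events (Section 9) places the examination at Visit 1, Visit 8 and early termination (ET).

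**Exposure and named reactions.** At Visit 3 (Section 8) the caregiver is observed "administering Test Product topically to the diabetic foot ulcer and surrounding intact skin". Appendix 2 says: "Local reactions to test product administration include but are not limited to pain, edema, rash, cellulitis, localized infectious processes"; these count as adverse events.

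**Primary objective.** Section 4 and the synopsis list five safety variables. Physical examination is one, and *Local wound/skin assessments* is another.

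**SAP.** Under Analysis, in the part on other safety data: "Table describing changes noted in physical examinations (at each visit after randomization) will be constructed for each subject". The caption of Shell Table 6, which holds these changes, adds: "If there is no change, entry will be blank". That shell numbers the randomization visit as 1 and continues through all scheduled post-baseline visits.

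**The concern.** Safety and tolerability of a topical product is the primary objective, and the skin around the ulcer is exposed twice daily for 28 days. Two of the five primary-objective variables could in principle deliver systematic skin data, yet neither is written so that a site must examine skin.

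Three things are at stake:

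- **Comparability.** With up to five sites using their own examination practice, how hard anyone looks at the skin may differ by site. The escalation decision from 5% to 10% rests on one cohort of 12 active and 4 placebo subjects, so a few missed or unevenly recorded skin findings matter.
- **Baseline.** Appendix 2 does not count a pre-existing condition that fluctuates without worsening, but does count a condition first detected after dosing even if it may have been present before. Applying either rule to skin needs a pre-treatment skin record, and none is required.
- **Reporting.** A reader of Shell Table 6 cannot tell a normal examination from one that was never done.

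**Working it through.** No sample size, power or event rate enters this point. The check is to set the texts side by side and count.

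**Step 1. Is skin in the required examination?** Systems listed in Section 11.5.1: 8. Skin entries: 0.

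**Step 2. Does the separate skin variable close the gap?** Section 11.5 says the time points of all safety assessments are in the Schedule of Events, so a working variable should be traceable there.

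| Where it should appear | What is found |
|---|---|
| Section 4 and synopsis, primary objective | *Local wound/skin assessments* listed |
| Section 11.5 subsections | Physical examination, vital signs, ECG, laboratory; none for skin |
| Schedule of Events | Visual examination of the ulcer at Visits 1 to 8 and ET; no skin row |
| Section 8, visit procedures | Visual examination of the ulcer; no skin examination |
| SAP Analysis and shell tables | No table for skin or local assessments |

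The variable is named, but it is not defined, scheduled under its own name, or tabulated.

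**Step 3. What would Shell Table 6 print for a completer?**

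- Visits from randomization on, as the shell counts them: Visits 3 to 8, so 8 − 3 + 1 = 6.
- Of these, visits with a scheduled physical examination: Visit 8 only, so 1.
- Entries with no examination behind them: 6 − 1 = 5 (Visits 3 to 7).
- If the randomization visit is left out, as the SAP text may be read: 5 visits, 1 examined, 5 − 1 = 4 unexamined.

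If all 32 planned subjects complete, that is 5 × 32 = 160 of 6 × 32 = 192 subject-visits (or 4 × 32 = 128 of 5 × 32 = 160). Each would be blank, and the SAP gives a blank the meaning of no change. This affects every body system, not only skin. It is also a direct mismatch between the SAP and the Schedule of Events.

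**Step 4. Would adding skin to Section 11.5.1 be enough?** For a completer it adds a Visit 1 record and one post-baseline look, at Day 42. Treatment ends on Day 28, so that look comes 42 − 28 = 14 days later (visit windows aside), when a reaction during dosing may have resolved. Using the visits at which the ulcer is already inspected gives looks at Visits 4, 5, 6 and 7, which are 4 records during or at the end of dosing.

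**The case against.** The strongest reply is that skin is covered by other routes, and much of it stands.

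- The list is a floor. A site whose own practice includes skin will examine it. The documents show neither those practices nor the eCRF, so one can say that skin may go unexamined, not that it will.
- The ulcer is inspected at every visit. Appendix 4 has the investigator or designee cleanse the ulcer and the area around it, and has surrounding skin prepared before light debridement. Local and systemic adverse events are recorded at Visit 1 and Visits 3 to 8, and Section 11 makes the investigator responsible for detecting them.
- Photographs of the site, two from 18 inches and one close-up, are taken before treatment. How much surrounding skin is in frame is not stated.
- The SAP's primary endpoint analysis is treatment-emergent adverse event incidence. Shell Table 6 belongs to other safety data. A rash recorded as an event reaches the primary table whatever Shell Table 6 prints.

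A reader might therefore infer either that the primary safety analysis cannot see skin reactions or that nothing is missing. The documents support neither. The event route is real, but Section 11 has events reported by the subject or caregiver, and Section 11.2 prefers open-ended questions. That is not a systematic examination, and it supplies no required baseline.

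A reader might also infer that rash and cellulitis are the expected reactions to this gel. Appendix 2 gives them only as non-exhaustive examples of what counts as an adverse event. The protocol says "reasonably expected adverse events of LA-Bisphosphocin-Nu-3 gel may be found in the Investigator's Brochure", and that brochure is not among the documents.

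**Conclusion.** The point holds in a limited form. The plan requires no systematic skin examination: the minimum list omits skin, and the primary-objective variable that names skin is never made operational. The consequence is uneven, event-driven ascertainment and no required baseline skin record. It is not the loss of skin reactions from the primary analysis.

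The reporting fault is firmer. For a completer, 5 of 6 Shell Table 6 entries (4 of 5 on the narrower reading) would stand as unchanged with no physical examination of any system done. This assumes that sites follow the Schedule of Events, do no extra examinations, and that the table is built as the shell shows.

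How many skin findings would be missed cannot be estimated from the documents, because it depends on site practice. The gap is worth closing because the trial's purpose is topical safety, the groups are small and the change is cheap.

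**What to change.** 1. Protocol Section 11.5.1: add skin, including peri-ulcer skin, to the minimum list.
2. Make *Local wound/skin assessments* operational: define it, give it a Schedule of Events row, and record peri-ulcer skin as normal, abnormal or not done at the visits where the ulcer is already visually examined (Visits 1 to 8 and ET).
3. SAP: add a table of this variable by treatment group and visit.
4. SAP Shell Table 6: add a not-examined code, and restrict the table to visits with a scheduled physical examination.
5. Reconcile Protocol Sections 4, 9 and 11.5.1 with the SAP Analysis text and Shell Table 6, so that the visits and variables agree.

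The cost is one more eCRF field per visit, at most 8 × 32 = 256 entries if all 32 subjects complete, one extra SAP table, and a few more minor findings to record. No extra visit is needed.
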